## **SAE and Pregnancy Reporting Contact Information**

### Suggested Reporting Form:

- SAE Report Form (provided by Takeda)
- US FDA MedWatch 3500A:
- Any other form deemed appropriate by the sponsor-investigator

### **Product Complaints**

A product complaint is a verbal, written, or electronic expression that implies dissatisfaction regarding the identity, strength, purity, quality, or stability of a drug product. Individuals who identify a potential product complaint situation should immediately contact Takeda and report the event. Whenever possible, the associated product should be maintained in accordance with the label instructions pending further guidance from a Takeda Quality representative.

### **For Product Complaints**

[REDACTED] – 7 p.m. ET

Product complaints in and of themselves are not AEs. If a product complaint results in an SAE, an SAE form should be completed and sent to Takeda Pharmacovigilance

### Procedures for Reporting Drug Exposure During Pregnancy and Birth Events

If a woman becomes pregnant or suspects that she is pregnant while participating in this study or within 90 days after the last dose, she must inform the investigator immediately and permanently discontinue study drug. The sponsor-investigator must immediately fax a completed Pregnancy Form to the Takeda Department of Pharmacovigilance or designee (see Section 8.2). The pregnancy must be followed for the final pregnancy outcome.

If a female partner of a male patient becomes pregnant during the male patient's participation in this study, the sponsor-investigator must also immediately fax a completed Pregnancy Form to the Takeda Department of Pharmacovigilance or designee (see Section 8.2). Every effort should be made to follow the pregnancy for the final pregnancy outcome.

Suggested Pregnancy Reporting Form:

Pregnancy Report Form (provided by Takeda)

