## 8.0 Dosage Modification Based on Adverse Events

Strictly follow the modifications in this table for the first **two** cycles, until individual treatment tolerance can be ascertained. Individual drugs can be dose reduced as per the table below depending on the adverse event attribution. If the toxicity is attributable to one drug, only that needs to be dose reduced. If overlapping toxicities are observed, the dose reductions can be alternated between the suspected drugs, starting with the drug most likely related to the adverse event. Thereafter, these modifications should be regarded as guidelines to limit to mild-to-moderate, but not debilitating, side effects. If multiple adverse events are seen, administer dose based on greatest reduction required for any single adverse event observed. Reductions apply to treatment given in the preceding cycle and are based on adverse events observed since the prior dose.

**NOTE: If ixazomib, lenalidomide or daratumumab is discontinued, the patient can continue on the other drugs, unless specified otherwise in the dose modification tables. If all three are discontinued, the patient will go to event monitoring (Section 4.2).**

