#### Pregnancy

All initial reports of pregnancy must be reported to Janssen Scientific Affairs, LLC by the PRINCIPAL INVESTIGATOR **within 24 hours of becoming aware of the event** using the Serious Adverse Event Form. Abnormal pregnancy outcomes (e.g. spontaneous abortion, fetal death, stillbirth, congenital anomaly, ectopic pregnancy) are considered serious adverse events and must be reported using the Serious Adverse Event Form.

Any subject who becomes pregnant during the study must be promptly withdrawn from the study and discontinue further study treatment.

Because the effect of the Janssen medicinal product on sperm is unknown, pregnancies in partners of male subjects exposed to a Janssen medicinal product will be reported by the PRINCIPAL INVESTIGATOR **within 24 hours of their knowledge of the event** using the Serious Adverse Event Form. Depending on local legislation this may require prior consent of the partner.

Follow-up information regarding the outcome of the pregnancy and any postnatal sequelae in the infant will be required.

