#### Before starting study drug:

##### *Female Subjects:*

- FCBP must have two negative pregnancy tests (sensitivity of at least 50 mIU/mL) prior to starting lenalidomide. The first pregnancy test must be performed within 10-14 days prior to the start of lenalidomide and the second pregnancy test must be performed within 24 hours prior to the start of lenalidomide. The subject may not receive study drug until the Investigator has verified that the results of these pregnancy tests are negative.
- Will be warned that sharing study drug is prohibited and will be counseled about pregnancy precautions and potential risks of fetal exposure..
- Must agree to abstain from donating blood during study participation and for at least 28 days after discontinuation from the study.

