#### During study participation and for 28 days following discontinuation from the study:

##### *All Subjects:*

---

† A female of childbearing potential is a sexually mature woman who: 1) has not undergone a hysterectomy or bilateral oophorectomy; or 2) has not been naturally postmenopausal for at least 24 consecutive months (i.e., has had menses at any time in the preceding 24 consecutive months).

- Only enough lenalidomide for one cycle of therapy may be dispensed with each cycle of therapy.
- If pregnancy or a positive pregnancy test does occur in a study subject or the partner of a male study subject during study participation, lenalidomide must be immediately discontinued.

*Female Subjects:*

- FCBP with regular or no menstrual cycles must agree to have pregnancy tests weekly for the first 28 days of study participation and then every 28 days while on study, at study discontinuation, and at day 28 following discontinuation from the study. If menstrual cycles are irregular, the pregnancy testing must occur weekly for the first 28 days and then every 14 days while on study, at study discontinuation, and at days 14 and 28 following discontinuation from the study.
- In addition to the required pregnancy testing, the Investigator must confirm with FCBP that she is continuing to use two reliable methods of birth control at each visit.
- Counseling about pregnancy precautions and the potential risks of fetal exposure must be conducted at a minimum of every 28 days. During counseling, subjects must be reminded to not share study drug and to not donate blood, .

Pregnancy testing and counseling must be performed if a subject misses her period or if her pregnancy test or her menstrual bleeding is abnormal. Study drug treatment must be discontinued during this evaluation.

- Females must agree to abstain from breastfeeding during study participation and for at least 28 days after discontinuation from the study.

*Male Subjects:*

- Counseling about the requirement for latex condom use during sexual contact with females of childbearing potential and the potential risks of fetal exposure must be conducted at a minimum of every 28 days. During counseling, subjects must be reminded to not share study drug and to not donate blood, sperm, or semen, .

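### Read literally, Section 10.61 permanently stops study drug when a woman only suspects pregnancy, even if testing then rules it out, which conflicts with Appendix V

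*Combined protocol and SAP*

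**What the plan says.** Four places in the protocol bear on this.

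- **Section 10.61**, the ixazomib supplier's reporting section, under the procedures for drug exposure during pregnancy. The trigger is "If a woman becomes pregnant or suspects that she is pregnant while participating in this study or within 90 days after the last dose", and the instruction is that "she must inform the investigator immediately and permanently discontinue study drug". The sentences that follow require a Pregnancy Form to be faxed and the pregnancy to be followed to its outcome.
- **Appendix V**, the lenalidomide pregnancy requirements, for the period on study: "Pregnancy testing and counseling must be performed if a subject misses her period or if her pregnancy test or her menstrual bleeding is abnormal". It adds: "Study drug treatment must be discontinued during this evaluation". For the period before treatment starts it says: "The subject may not receive study drug until the Investigator has verified that the results of these pregnancy tests are negative".
- **Section 10.62**, item 4, the daratumumab supplier's reporting section: "Any subject who becomes pregnant during the study must be promptly withdrawn from the study and discontinue further study treatment". It says nothing about suspicion.
- **Section 8.0**, on dose modification for adverse events: "If ixazomib, lenalidomide or daratumumab is discontinued, the patient can continue on the other drugs", unless the tables say otherwise, and "If all three are discontinued, the patient will go to event monitoring".

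**The concern.** A missed period is a common reason to suspect pregnancy, so the same event can bring one woman under both Section 10.61 and Appendix V. If her test is negative, the two texts point in different directions: the first has already stopped her drug for good, while the second tied the stop to an evaluation that is now over.

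At stake is myeloma treatment for a patient in whom there is no pregnancy to protect. An immediate stop while pregnancy is possible is right. A permanent stop after pregnancy has been excluded protects no fetus, and a rule of that kind may discourage a woman from voicing a suspicion early.

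It is also unclear which drugs she would lose, because the protocol does not use *study drug* in one sense. Section 7.2 uses it for ixazomib, Appendix V uses it directly after the tests required before lenalidomide, and the Appendix VI diary lists lenalidomide, ixazomib and dexamethasone under it.

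**Working it through.** The point turns on wording, and the plan gives no figure to reproduce. The check sets the provisions side by side and then follows one case through them.

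| Provision | Trigger | Action | After a negative test |
|---|---|---|---|
| 10.61 | Pregnancy or suspicion of it | Permanent stop of study drug | No exception |
| Appendix V, on study | Missed period, abnormal test or abnormal bleeding | Test, counsel, stop during the evaluation | Restart implied, not stated |
| Appendix V, before start | Start of lenalidomide | No drug until tests are verified negative | Drug may be given |
| 10.62, item 4 | Actual pregnancy | Withdraw and stop all study treatment | Not applicable |

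**Case: missed period, suspicion reported, test negative.**

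1. Section 10.61 is triggered by the suspicion. Its instruction is mandatory and permanent, and nothing in the section lifts it when the test comes back negative.
2. Appendix V is triggered by the missed period. Its stop is limited to the evaluation. It has no sentence on restarting, but a stop with that limit implies that treatment may go on afterwards. The rule before first dosing, which makes a verified negative result the condition for receiving drug, points the same way, although it is not a rule on resuming.
3. Section 10.62 is not triggered, because she is not pregnant.
4. No clause ranks these sections.

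**Confirmed pregnancy.** Sections 10.61 and 10.62 both end treatment, and Appendix V stops lenalidomide on pregnancy or a positive test. That case is outside the point.

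**Consequence for the woman.** Section 8.0 was written for adverse events; applying it here is an extension. If it is applied and *study drug* means ixazomib alone, she loses ixazomib and may stay on the rest. If the term covers the whole regimen, she goes to event monitoring and protocol treatment ends.

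**How many women.** Planned female accrual is 28 of 80 (Section 16.631), and median age at onset is 65 to 70 years (Section 1.1). The documents do not give the share of childbearing potential, so 0% to 10% is an assumption:

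- 0%: 28 × 0.00 = 0
- 5%: 28 × 0.05 = 1.4
- 10%: 28 × 0.10 = 2.8

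That is 0 to about 3 women over both arms. Only those with a suspected pregnancy that is later excluded would be affected.

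**The case against.** The strongest reply is that the Section 10.61 text is a reporting procedure and not a dosing rule. Its heading concerns reporting, and the Pregnancy Form and outcome follow-up make sense only for an actual pregnancy. A site would naturally combine the texts: stop, test under Appendix V, then report and stop for good if she is pregnant. This stands as evidence of intent, and it is why the wording is probably an oversight. It does not remove the explicit reference to suspicion or the word *permanently* from a sentence addressed to the patient's treatment.

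The reply also limits what can be claimed. A reader might infer any of the following, and the documents do not support them:

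- **That Appendix V grants an express right to restart.** It does not; restart is inferred from the time limit on the stop. The dose-modification tables define discontinuing as a total stop, although that definition belongs to their action column.
- **That nothing governs restart.** Sections 3.19c and 15.28 bind patients and prescribers to the Revlimid REMS program, whose full rules are not in the documents and may settle the matter for lenalidomide. They would not cure the wording of Section 10.61.
- **That she would certainly lose the whole regimen.** This depends on an undefined term and on extending Section 8.0 beyond adverse events.
- **That the reference to Section 8.2 bears on stopping or restarting drug.** In context it says where to send the form. It is a stale cross-reference and a separate editorial slip.

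Rarity is also a fair objection. With two contraceptive methods or abstinence required (Section 3.18) and scheduled pregnancy tests (Section 4.1, footnote 3), it is plausible that no patient is ever affected.

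**Conclusion.** The point holds as a minor wording conflict with a practical consequence. Section 10.61 requires a permanent stop on suspicion alone, Appendix V limits the stop to the evaluation, and Section 10.62 reserves the end of treatment for actual pregnancy. Followed to the letter, Section 10.61 gives a worse result than the other two sections for a woman in whom pregnancy has been excluded.

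The literal wording is certain; that it was meant is doubtful. The size, 0 to about 3 women who could ever come under the rule, rests on the assumed share of childbearing potential. A reader might infer that the trial's result is at risk. It is not: the definition of confirmed complete response, the 36 evaluable patients per arm and the threshold of 13 successes do not depend on this text.

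**What to change.** In the first paragraph of the Section 10.61 pregnancy procedures, keep the trigger (pregnancy or suspicion, on study or within 90 days of the last dose) and the duty to tell the investigator at once. Replace the permanent stop and the rest of that paragraph with:

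> All study drugs are held while pregnancy is evaluated (Appendix V). If pregnancy is ruled out, treatment may resume, with lenalidomide resumed subject to Revlimid REMS requirements. If pregnancy is confirmed, all study drugs are permanently discontinued, the Pregnancy Form is faxed immediately, and the pregnancy is followed to final outcome.

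Retain the addressee for the form. The paragraph on partners of male patients is unaffected. Naming all study drugs settles the scope for both the hold and the stop, and agrees with Section 10.62 for confirmed pregnancy. Moving the form and follow-up behind confirmation matters, because otherwise they would still follow from mere suspicion.

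The cost is a short amendment and possibly the ixazomib supplier's agreement, since this is its reporting section. Appendix V already requires the testing, so no test or visit is added. Holding the whole regimen is a choice; its price is a brief interruption of all drugs during the evaluation.

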### 10.62 Special reporting requirements for Janssen

#### **Overview**

As the sponsor of the Study, PRINCIPAL INVESTIGATOR shall be solely responsible for complying, within the required timelines, any safety reporting obligation to competent Health Authorities, IRB/ECs and any participating (co or sub) investigators, as defined in applicable laws and regulations. For the purposes of this section, safety data includes adverse events, product quality complaints (PQCs), and special situations including pregnancies.

The PRINCIPAL INVESTIGATOR will provide safety information to Janssen Scientific Affairs, LLC on adverse events, special situations including pregnancies and product quality complaints as defined within this section.

#### **1. Management of Safety Data**

This Study has been designated as an interventional study. As such, all adverse events for Janssen Medicinal Products regardless of causality and special situations excluding those from subjects not exposed to a Janssen Medicinal Product and product quality complaints with or without an adverse event as described in this Exhibit will be reported from the time a

subject has signed and dated an Informed Consent Form (ICF) until completion of the subject's last study-related procedure (which may include contact for follow-up safety). Serious adverse events will be reported for 30 days after the last dose of study drug.

For the purposes of this study, the Janssen medicinal product is: DARZALEX™ (daratumumab)

## **2. Definitions**

### **2.1. Adverse Event (AE)**

An adverse event is any untoward medical occurrence in a clinical study subject administered a medicinal (investigational or non-investigational) product. An adverse event does not necessarily have a causal relationship with the treatment. An adverse event can therefore be any unfavorable and unintended sign (including an abnormal finding), symptom, or disease temporally associated with the use of a medicinal (investigational or non- investigational) product, whether or not related to that medicinal (investigational or non-investigational) product. (Definition per International Conference on Harmonisation [ICH])

This includes any occurrence that is new in onset or aggravated in severity or frequency from the baseline condition, or abnormal results of diagnostic procedures, including laboratory test abnormalities.

### **2.2. Adverse Events of Special Interest**

Adverse events of special interest are events that Janssen Scientific Affairs, LLC is actively monitoring as a result of a previously identified signal (even if non-serious).

These adverse events are:

- Infusion reactions
- Infections
- Cytopenias
- HBV Reactivation
- Other malignancies

### **2.3. Individual Case Safety Report (ICSR)**

A valid ICSR must contain the four minimum criteria required to meet regulatory reporting requirements.

- an identifiable subject (but not disclosing personal information such as the subject's name, initials or address)
- an identifiable reporter (investigational site)
- a Janssen medicinal product
- an adverse event, outcome, or certain special situations

The minimum information required is:

- suspected Janssen medicinal product (doses, indication)
- date of therapy (start and end date, if available)
- batch or lot number, if available
- subject details (subject ID and country)
- gender
- age at AE onset
- reporter ID
- adverse event detail (AE verbatim in English), onset date, relatedness, causality, action taken, outcome, (if available)
- Janssen protocol ID

## 2.4. Product Quality Complaint (PQC)

A product quality compliant is defined as any suspicion of a product defect related to a potential quality issue during manufacturing, packaging, release testing, stability monitoring, dose preparation, storage or distribution of the product, or delivery system. Not all PQCs involve a subject. Lot and batch numbers are of high significance and need to be collected whenever available.

Examples of PQC include but not limited to:

- Functional Problem: e.g., altered delivery rate in a controlled release product
- Physical Defect: e.g. abnormal odor, broken or crushed tablets/capsules
- Potential Dosing Device Malfunction: e.g., autoinjector button not working, needle detaching from syringe
- Suspected Contamination
- Suspected Counterfeit

## 2.5. Serious Adverse Event (SAE)

A serious adverse event based on ICH and EU Guidelines on Pharmacovigilance for Medicinal Products for Human Use is any untoward medical occurrence that at any dose:

- Results in death
- Is life-threatening  
(The subject was at risk of death at the time of the event. It does not refer to an event that hypothetically might have caused death if it were more severe.)
- Requires inpatient hospitalization or prolongation of existing hospitalization
- Results in persistent or significant disability/incapacity
- Is a congenital anomaly/birth defect
- Is a suspected transmission of any infectious agent via a medicinal product
- Is medically important\*

\*Medical and scientific judgment should be exercised in deciding whether expedited reporting is also appropriate in other situations, such as important medical events that may not be immediately life threatening or result in death or hospitalization but may jeopardize the subject or may require intervention to prevent one of the other outcomes listed in the definition above. These should usually be considered serious.

**NOTE: DEATH FOR ANY REASON SHOULD BE REPORTED AS A SERIOUS ADVERSE EVENT.**

### 2.5.1. Hospitalization

For reports of hospitalization, it is the sign, symptom or diagnosis which led to the hospitalization that is the serious event for which details must be provided.

Any event requiring hospitalization or prolongation of hospitalization that occurs during the study must be reported as a serious adverse event, except hospitalizations for the following:

- Hospitalizations not intended to treat an acute illness or adverse event (e.g., social reasons such as pending placement in long-term care facility)

- Surgery or procedure planned before entry into the study. [Note: Hospitalizations that were planned before the start of data collection and where the underlying condition for which the hospitalization was planned has not worsened will not be considered serious adverse events. Any adverse event that results in a prolongation of the originally planned hospitalization is to be reported as a new serious adverse event.]
- [For convenience the investigator may choose to hospitalize the subject for the duration of the treatment period.]

### **2.5.2. Life-Threatening Conditions**

Disease progression should not be recorded as an adverse event or serious adverse event term; instead, signs and symptoms of clinical sequelae resulting from disease progression/lack of efficacy will be reported if they fulfill the serious adverse event definition.

### **3. Unlisted (Unexpected) Adverse Event/Reference Safety Information**

An adverse event is considered unlisted if the nature or severity is not consistent with the applicable product reference safety information. For a medicinal product(s) with a marketing authorization, the expectedness of an adverse event will be determined by whether or not it is listed in the applicable product information.

For DARZALEX™ (daratumumab), the expectedness of an adverse event will be determined by whether or not it is listed in the Investigator's Brochure

### **4. Special Reporting Situations**

Safety events of interest for a Janssen medicinal product that require expediting reporting and/or safety evaluation include, but are not limited to:

- Drug exposure during pregnancy (maternal and paternal)
- Overdose of a Janssen medicinal product
- Exposure to a Janssen medicinal product from breastfeeding
- Suspected abuse/misuse of a Janssen medicinal product
- Inadvertent or accidental exposure to a Janssen medicinal product
- Any failure of expected pharmacological action (i.e., lack of effect) of a Janssen medicinal product
- Medication error involving a Janssen medicinal product (with or without patient exposure to the Janssen medicinal product, e.g., name confusion)
- Suspected transmission of any infectious agent via administration of a medicinal product
- Unexpected therapeutic or clinical benefit from use of a Janssen medicinal product

These safety events may not meet the definition of an adverse event; however, from a Janssen Scientific Affairs, LLC perspective, they are treated in the same manner as adverse events. Special situations should be recorded on the Adverse Event page of the CRF.

Any special situation that meets the criteria of a serious adverse event should be recorded on a Serious Adverse Event Report Form and be reported to Janssen Scientific Affairs, LLC **within 24 hours of becoming aware of the event.**

